## 2 STUDY OBJECTIVE

This prospective, multicenter observational study will examine the ability of ECGi mapping to

- 1) Effect of Ibutilide on the number and size of the driver domains
- 2) Effect of ablation of Ibutilide-organized driver domains
- 3) Effect of PV isolation on driver domains

We hypothesize that this approach will lead to successful arrhythmia control

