## 6 ENDPOINTS

### 6.1 Primary Endpoint

Primary Endpoints:	1. Acute Procedural Outcome Analysis: after performing procedures on the 20 patients 2. Clinical Outcome Analysis - Freedom from recurrent At/AF at 12 months
Additional Endpoints:	1. Effect of PV isolation on driver domains 2. Number/Size of drivers identified/ablated baseline 3. Percentage reduction of driver regions (site and size) after ibutilide 4. AF termination rate (to AT/SR) 5. Post-ablation inducibility of sustained AF (>5 mins) with isuprel 6. Post-ablation inducibility of AF with (>5mins) burst pacing 7. Total duration of RF ablation/ Fluro time/exposure/ procedure time

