#### Other mapping and protocols

Isoprenaline challenge for trigger mapping or for induction of sustained atrial fibrillation

- The infusion can be used for doses as high at 30mcg/kg/min and should be continued for 10-30 minutes to truly assess the effect of isoprenaline. Trigger mapping requires the operators to use at least 20 mcg/kg/min or maximum tolerated dose for 10-20 minutes. When isoprenaline is used to sustain AF in cases where AF induced by pacing is nonsustained then lower doses can be used – 2-4 mcg/kg/min

AF induction and cardioversion- Induce atrial fibrillation by rapid pacing in the atrium. Once sustained AF is noted- then perform DCCV and wait to see if triggers are seen inducing atrial fibrillation.

- **Presenting rhythm- Sinus- Induce AF – is sustained >15 mins**
  - Map sinus acquired first and then Map induceAF will be acquired
- **Presenting rhythm- Atrial fibrillation**
  - Map spontAF will be acquired  
PV isolation is initially completed with standard approach
  - If AF persists then

- Progressive doses of Ibutilide should be administered (0.25mg, then 0.25mg, then 0.5mg) and repeat ECGi mapping (MapIbutilide0.25, MapIbutilide0.50 & MapIbutilide1.00) should be performed. If the rhythm organizes to atrial tachycardia this will be ablated and if rhythm converts to sinus – then procedure is deemed complete.

If still in AF, Driver regions are targeted  
(Right and left atria)

Prior to ablation- LAA and RAA cycle length are to be measured over 10 beats

Ablation of drivers can be initiated in chamber with faster CL or with greater number of identified drivers. Drivers can be addressed in order of importance as suggested by maps.

Periodic reassessment of TCL in LAA and RAA to be done to help direct operator to chamber of interest- e.g. if there is significant gradient between RAA and LAA such that RAA is faster then drivers can be pursued in RAA prior to completion of all driver regions of LA

All drivers are to be sequentially ablated; if rhythm is still not organized then ablation sites are visited again to ensure adequate ablation. If AF persists, ECGi mapping should be repeated (MapRe1,2.) and additional driver regions can be targeted

- **Ibutilide Dosing Guidelines**

1. Patients <60 kg – Ibutilide dosing is limited to a maximum dose of 0.50
2. Patients >60 kg are allowed to receive full dosing of ibutilide up to 1.0mg

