## 17 DATA ANALYSIS

Baseline clinical characteristics (e.g. age, gender, renal function) and procedural characteristics (e.g. surface intracardiac electrogram, and imaging findings) of the patients will be collected and analyzed. All continuous variables will be performed as the mean  $\pm$  standard deviation, and all categorical variables as a percentage of the total study population.

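### The AF termination endpoint names no procedural step and falls under an all-patient denominator, so it describes the whole strategy and does not answer Objective 2

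*Combined protocol and SAP*

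**What the plan says.** Section 2 lists three objectives. The second is "Effect of ablation of Ibutilide-organized driver domains". The same section gives a hypothesis about the approach as a whole: "We hypothesize that this approach will lead to successful arrhythmia control".

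Section 6.1 lists, as additional endpoint 4, "AF termination rate (to AT/SR" (the closing bracket follows in the protocol). It states no step, time point or denominator.

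Section 10.3, under the heading Other mapping and protocols, sets out the order of the procedure:

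- First, "PV isolation is initially completed with standard approach".
- If AF persists, ibutilide is given in up to three increments, with repeat mapping. At this stage, "If the rhythm organizes to atrial tachycardia this will be ablated and if rhythm converts to sinus – then procedure is deemed complete".
- Only then, "If still in AF, Driver regions are targeted".

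Section 17 is the whole of the analysis text. Continuous variables are summarized by mean and standard deviation, and "all categorical variables as a percentage of the total study population". The protocol summary marks both the primary and the secondary analytical analysis as not applicable. Section 8 sets the sample at 20 patients on grounds of feasibility.

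**The concern.** AF can end at three points in this procedure, and only the last of them is the intervention named in Objective 2. A patient who converts on ibutilide has no driver ablated, yet can count as a termination under endpoint 4. Followed as written, the plan gives one percentage that pools PVI, drug and driver ablation. If only driver-step terminations were counted in the numerator, section 17 would still divide them by a population that includes patients who never reached that step.

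The other objectives fare better. Objective 1 has an endpoint on driver reduction after ibutilide, and Objective 3 has one on the effect of PVI on driver domains. For Objective 2, additional endpoint 2 counts drivers identified and ablated but not what ablating them achieved. Inducibility, procedure times and 12-month freedom from AT/AF describe the complete procedure.

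At stake is whether the report can say that AF ended before or during driver ablation. Section 3 presents the study as a small mechanistic one, and this is one of its three stated questions. In an unblinded study with no rule in place, the choice of step, the denominator and the handling of AT on ibutilide could all be settled after the results are known.

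**Working it through.** The plan contains no calculation to reproduce. The check compares endpoints with procedural steps and then shows, with assumed counts, how far the two rates can differ.

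**Inputs**

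- N = 20 (section 8). I take all 20 as treated and in AF when PVI begins (assumption).
- T = 13 terminations in total (assumption; the documents give no such count).
- s = number who leave AF at PVI or on ibutilide, before driver ablation (assumption; 0, 4 and 8 are shown). Each of these counts as a termination, because endpoint 4 accepts either AT or sinus rhythm.

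**Formulas**

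- Planned all-patient rate = T/N.
- Driver-step rate = (T − s)/(N − s): terminations during driver ablation over patients still in AF when it starts.
- Driver-step terminations over everyone = (T − s)/N: the result if section 17's denominator is kept and only the numerator is restricted.
- Intervals are exact (Clopper–Pearson) 95%.

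**Results**

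The planned rate is the same in every row: 13/20 = 65% (CI 40.8–84.6%).

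| Left AF before driver ablation (s) | Driver-step rate | Exact 95% CI | Driver-step terminations over 20 |
|---|---|---|---|
| 0 | 13/20 = 65% | 40.8–84.6% | 13/20 = 65% |
| 4 | (13 − 4)/(20 − 4) = 9/16 = 56% | 29.9–80.2% | 9/20 = 45% |
| 8 | (13 − 8)/(20 − 8) = 5/12 = 42% | 15.2–72.3% | 5/20 = 25% |

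**Reading the table.** One reported 65% is compatible with each of these driver-step rates. The rates agree only when nobody leaves AF early. Restricting the numerator alone does not repair this: with s = 8, driver ablation ends AF in 5 of the 12 patients who receive it (42%), but the figure over 20 is 25%. The intervals are wide and overlap throughout. The difference is therefore one of meaning, not something a sample this size could show statistically.

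**The case against.** **Section 17 does not mention AF termination.** Its first sentence concerns baseline and procedural characteristics, so the denominator rule reaches endpoint 4 only through its general wording. This stands as a caution. But the rule covers all categorical variables and no other rule exists. If it does not apply, endpoint 4 has no denominator at all, and the same amendment is needed.

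**Primary endpoint 1 could hold the step result.** The acute procedural outcome analysis is undefined, so a driver-step rate could be placed there. That is true, and it is why one should not say that the plan rules out an answer to Objective 2. As written, it does not require one.

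**The all-patient rate is legitimate.** It matches the hypothesis in section 2, and section 3 quotes 66% acute termination in an earlier study for PVI and driver ablation combined. This stands in full: the planned rate is not wrong and should be kept.

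**The data are probably recoverable.** Mapping after each ibutilide increment and cycle-length measurement before ablation should leave a record of rhythm. That reduces the harm, but nothing requires the counts to be reported.

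**Two stronger readings are tempting.** A reader might infer that the headline rate could hide a driver ablation that does nothing. The arithmetic allows it (if all 13 left AF early, the driver step would be 0/7), but nothing in the documents makes such a split likely.

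A reader might also infer that the driver-step rate could exceed the all-patient rate, because patients presenting in sinus rhythm might never have sustained AF ("Presenting rhythm- Sinus- Induce AF – is sustained >15 mins"). The documents give this little support. The same section allows isoprenaline to sustain AF when pacing-induced AF is nonsustained, eligibility requires persistent AF, and the step sequence is printed under the branch for patients presenting in AF. No scenario here rests on that inference.

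**Conclusion.** The concern holds as a gap between endpoint and objective. Endpoint 4 has no step, and the only denominator rule counts every patient, including those who never had a driver ablated. The resulting rate summarizes the strategy and leaves Objective 2 without a planned result that answers it.

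The size is illustrative only. With 13 of 20 terminations, the driver-step rate falls from 65% to 56% or 42% as four or eight patients leave AF earlier, and it does not differ if none do. This assumes that all 20 start in AF and that early exits count as terminations.

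The amendment should be made, but the point threatens neither safety nor the 12-month endpoint. Nor would a step-specific rate establish an effect of driver ablation, because there is no control group and the step follows PVI and ibutilide in the same patients.

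**What to change.** 1. Keep the termination rate over all patients as the result for the strategy.
2. Record rhythm (AF, AT or sinus) on the case report form at the end of PVI, of ibutilide and of driver ablation.
3. Amend section 17 and endpoint 4 so that termination at each of these three steps is reported as x/n, with n the patients in AF when that step began.
4. For Objective 2, report termination during driver ablation over all patients who start it, with an exact 95% CI. Show patients who organized to AT on ibutilide, and had the AT ablated, on a separate line.
5. State that the Objective 2 group is small, selected as non-responders to PVI and ibutilide, still under drug effect and uncontrolled, so that its rate is descriptive.

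Intervals for each ibutilide dose are more than an exploratory study of 20 needs.

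The cost is a few lines of analysis text and one rhythm field per step, with no added procedures or patients. The drawback is a smaller denominator and a wide interval: 5/12, for example, runs from 15% to 72%.
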